To address aim 2: To determine the effect that the stress management intervention has on the primary measured outcome: symptom free days. Other patient/family-centered outcomes will include parent stress, quality of life, asthma morbidity, healthcare utilization, and medication adherence. Baseline demographic characteristics will first be compared in univariate fashion between the two groups using the chi-squared test for categorical variables and the t-test for continuous variables. If any variable is not balanced by randomization, it will be used as a covariate in all secondary analyses. To test the hypothesis that the time average of number of symptom-free days over a two week period (primary outcome) at 3 and 6 month follow-up will be significantly higher among parents in Arm 2 (intervention) than in Arm 1 (usual care), a two sample t-test will be used to compare difference of mean symptom-free days over a two week period between the two arms with point estimates, 95% CI and p values being reported. Depending on the degree of dispersion, we may need to employ a Poisson or negative binomial model.

In secondary analysis, we will further explore the effect of the intervention by fitting random effect mixed models that (1) adjust for baseline covariates of interest, considered *a priori* or that differ between groups at baseline and are relevant to change in symptom-free days; (2) test for interaction between treatment effects and other covariates; and (3) examine patients who complete intervention and follow-up (per protocol analysis).

For continuous secondary outcomes, we will use the same approach as described above. For the categorical secondary outcomes, we will use the chi square test of whether relative rates between groups differ from 1. All subsequent estimates of relative rates (RR) will be adjusted (at the minimum) for age, sex, race/ethnicity and other covariates using generalized estimating equations (GEE). All estimates of RR will be reported with 95% confidence intervals (CIs). For measures of healthcare

utilization, the analysis will compare adjusted rates and RRs at 3 and 6 follow up. Depending on the degree of dispersion in the rates, these models will be based on either Poisson or negative binomial regression models.

Sensitivity analyses will be conducted to account for missing data. These will estimate the highest and lowest potential treatment effect for primary and secondary outcomes.

Missing Data

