Baseline Sociodemographic factors	Age, gender, race, ethnicity, insurance type, parent education, household income, family medical history, parent health literacy, parental resilience
Intervention uptake, satisfaction, and fidelity	Completion of 1:1 session, completion of group sessions, location/format of sessions, use of stress management techniques, use of techniques with children
Asthma severity	
 • NAEPP classification, as determined by IMPACT DC clinician
Asthma control	
 • NAEPP classification, as determined by IMPACT DC clinician • ACT score

Table of Planned Analyses

Breathe with Ease: A Unique Approach to Managing Stress (BEAMS)

PI: [name], MPH

Final 11.25.16

We will examine interactions between primary and secondary outcomes and

- baseline asthma variables (severity/control, health care utilization, exacerbations),
- baseline psychosocial variables (parental stress and depression, resilience, child anxiety and depression, quality of life)
- baseline demographic factors

In addition, we will examine interactions between primary and secondary outcomes and intervention uptake within the intervention group.

Key planned analyses include:

- Interaction between primary outcome and parental age, education, household income, child age and gender
- Interaction between primary outcome and baseline child asthma severity, control, and history of unscheduled healthcare utilization
- Interaction between primary outcome and baseline parental depression
- Interaction between primary outcome and baseline parental stress
- Interaction between primary outcome and baseline parental resilience
- Interaction between primary outcome and baseline child depression
- Interaction between primary outcome and baseline child anxiety
- Interaction between primary outcome and baseline asthma severity/control
- Dose-response analysis of intervention uptake (session completion and parent report of technique utilization)

Sample Size Calculation: The sample size was recalculated on September 14, 2015 based on the baseline data collected from the first 60 participants, which showed the following:

- mean = 10.25 days
- standard deviation = 4.12
- median = 11.5 days.

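### Baseline balance tests choose covariates for the secondary analyses, so the adjustment set is not fixed in advance and precision is lost

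*Protocol*

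**What the plan says.** Protocol section D.10, under aim 2, starts with a comparison of the arms: "Baseline demographic characteristics will first be compared in univariate fashion between the two groups using the chi-squared test for categorical variables", with t-tests for continuous variables. It then states: "If any variable is not balanced by randomization, it will be used as a covariate in all secondary analyses." No threshold for imbalance is given.

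The next paragraph sets a different rule for the secondary mixed models. They are to "adjust for baseline covariates of interest, considered *a priori* or that differ between groups at baseline and are relevant to change in symptom-free days". The a priori covariates are not named.

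Relative rates are to be "adjusted (at the minimum) for age, sex, race/ethnicity and other covariates using generalized estimating equations (GEE"). The additional covariates are again unnamed.

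The SAP table has a block of control variables. Its sociodemographic row reads: "Age, gender, race, ethnicity, insurance type, parent education, household income, family medical history, parent health literacy, parental resilience". The block also holds NAEPP severity, NAEPP control and the ACT score, as well as intervention uptake, satisfaction and fidelity. The SAP does not say which of these enter which model.

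The primary comparison is unadjusted: "a two sample t-test will be used to compare difference of mean symptom-free days over a two week period between the two arms", with a Poisson or negative binomial model as a possible alternative.

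**The concern.** In a properly randomised trial every baseline difference is due to chance. A significance test on that difference says nothing about whether the variable predicts the outcome, and only prediction makes adjustment worthwhile. A rule triggered by the test therefore lets in variables with no prognostic value and gives a strong predictor no place unless it happens to be unbalanced.

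The two rules in D.10 also disagree. One admits any unbalanced variable to every secondary analysis. The other requires a variable to be both unbalanced and relevant, or else chosen beforehand from a list that is not given. Two analysts following D.10 could fit different models to the same data. At stake are the precision of the adjusted secondary estimates and the ability to say before unblinding which model will be reported.

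**Working it through.** **1. How often chance flags a variable.** Inputs: the ten sociodemographic items in the SAP. Race and insurance type are nearly constant because of the eligibility criteria in Protocol section D.4, which leaves about eight informative items. The 0.05 threshold is assumed from the general alpha, and the tests are treated as independent. P(at least one flag) = 1 − 0.95^k.
- k = 8: 1 − 0.95^8 = 0.337; expected number of flags 8 × 0.05 = 0.40.
- k = 10: 1 − 0.95^10 = 0.401; expected number 0.50.

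**2. The plan's own figure first.** The Protocol gives a total of 152 for a difference of 1.0 day, SD 2.7, within-subject correlation 0.3, two assessments, 80% power and two-sided 0.05. The variance factor for the mean of two assessments is (1 + 0.3)/2 = 0.65. With (1.960 + 0.842)² = 7.849, n per arm = 2 × 2.7² × 0.65 × 7.849 / 1.0² = 74.4, rounded up to 75, so 150 in total. That is within 2 of the stated 152.

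**3. What the baseline value would add.** Assume that the documents' correlation of 0.3 also holds between baseline and each follow-up. Adjusting for baseline changes the factor to 0.65 − 0.3² = 0.56, a variance ratio of 0.56/0.65 = 0.862. Then n per arm = 2 × 2.7² × 0.56 × 7.849 = 64.1, rounded up to 65, so 130 in total instead of 150. Over assumed correlations from 0.1 to 0.5 the ratio runs from 0.98 to 0.67. This sizes the gain on symptom-free days; other outcomes will have their own correlations.

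**4. What the imbalance rule recovers.** Simulation of 20,000 trials per setting: 94 per arm (188 in total, 1:1 assumed), one outcome, one baseline covariate, and a standardised difference of 0.15 × 10.25 / 4.12 = 0.37.

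| Covariate-outcome correlation (assumed) | Never adjust | Adjust only if baseline p < 0.05 | Always adjust |
|---|---|---|---|
| 0.3, power | 72.0% | 72.4% | 75.9% |
| 0.5, power | 72.4% | 73.4% | 83.1% |
| 0.3, type I error | 5.1% | 4.8% | 4.9% |
| 0.5, type I error | 4.8% | 4.1% | 4.7% |

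The imbalance rule performs almost like no adjustment. Type I error is at or slightly below nominal.

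**5. The second rule, read at its worst.** Suppose relevance were judged on trial data: a variable enters if baseline p < 0.05 and its association with the outcome has p < 0.05. With ten covariates, one of them prognostic, and 93 per arm (6,000 trials), type I error was 4.9% at correlation 0.3 and 4.3% at 0.5. There was no inflation here either.

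**The case against.** Balance tests are not the only route to adjustment. D.10 allows covariates chosen a priori and fixes a minimum set for relative rates, and the SAP lists education, income, severity, control and ACT score. A reader might infer that prognostic variables are simply left out; the documents do not support that. They do leave those variables unattached to any model, and neither document names the baseline value of an outcome as an adjustment covariate. A mixed model could carry baseline as one of its repeated responses, but D.10 does not say so.

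A reader might also infer that the outcome data select the model, from the words "or that differ between groups at baseline and are relevant to change in symptom-free days". The text does not say whether relevance is judged on trial data or beforehand. It applies only to the mixed models, and only jointly with imbalance. It permits outcome-driven selection without stating it.

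A third inference would be that the p-values and confidence intervals become unreliable. The simulations do not support this: type I error stays at about 4–5% under either rule.

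The scope is limited too. For continuous secondary outcomes, "For continuous secondary outcomes, we will use the same approach as described above", which begins with an unadjusted t-test, and categorical ones begin with a chi-squared test. The power comparison models the imbalance rule alone, so any a priori covariate actually used would narrow the gap. At correlation 0.3, the only correlation the documents give, the gap is about 3 to 4 points. All of this limits the size of the point, but none of it makes balance testing a sound way to choose covariates.

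**Conclusion.** The point holds for the adjusted secondary analyses. D.10 states a selection rule that is driven by chance, sets a second rule beside it that does not agree, and leaves the remaining covariates unnamed. The SAP list does not close the gap, because it is not mapped to models and mixes baseline items with uptake, satisfaction and fidelity, which arise after randomisation.

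The size is modest to moderate: about 3.5 power points forgone at correlation 0.3 (75.9 − 72.4) and about 10 at 0.5 (83.1 − 73.4). This assumes one covariate, 94 per arm, a 0.05 imbalance threshold and those correlations. The harm is lost precision and an adjustment set that cannot be known in advance. False positives are not inflated, and the unadjusted primary t-test lies outside the rule. The change should be made, but the trial's main conclusion does not depend on it.

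**What to change.** In Protocol D.10:
- Present baseline data descriptively and remove balance testing as a way of selecting covariates.
- Delete "or that differ between groups at baseline and are relevant to change in symptom-free days" from the mixed-model sentence, and delete the open-ended reference to further covariates from the relative-rate sentence.
- Name one fixed baseline set for all adjusted secondary models: the baseline value of the outcome being analysed, plus variables the SAP already lists. Examples are child age, child sex, parent education, household income, and NAEPP severity and control at enrolment. Race adds almost nothing, since eligibility holds it nearly constant.

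In the SAP, assign the control variables to models, and keep uptake, satisfaction and fidelity out of every model that estimates the treatment effect.

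The cost is a few lines of text and no new data collection. The small downside is that a chance imbalance in an unlisted variable stays unadjusted; one labelled sensitivity analysis can show its effect.

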This study is a single blind, prospective randomized controlled trial comparing the IMPACT DC Asthma Clinic intervention of guideline-based clinical care, education, and short-term care coordination (usual care) to usual care plus parental stress management in a cohort of up to 250 parent-child dyads.

This study will employ a parallel-groups RCT design. Outcomes data will be collected by interviews at enrollment (baseline), 3 months post-enrollment, 6 months post-enrollment, and 12 months post-enrollment. The 12 month follow-up data will be collected only for a subset of participants.

D.2. Usual Care

All participants in both the usual care and intervention arms of the study will receive guideline-based asthma care in the IMPACT DC Asthma Clinic, supplemented by three months of limited care coordination services to address barriers to care.

The IMPACT DC Asthma Clinic is a fully validated and bilingual clinical intervention³³ that has operated at Children's National since 2004. It focuses on at-risk youth with an over-dependence on EDs for episodic care. It provides care to approximately 1000 new patients per year, and has won multiple national and local awards, including the EPA's 2006 National Environmental Leadership Award in Asthma Management, the 2012 DC Chartered Healthcare "*Making a Difference*" Health Disparities Award, and the 2012 DC Hospital Association *Haynes Rice Community Service Award*.

IMPACT DC's conceptual model begins with the premise that effective longitudinal asthma care is a broad continuum involving the child surrounded by his/her family, primary medical care home, hospital, ED, community pharmacist, insurance case manager, and school nurse. The vision continues with the novel idea that the ED can and should be a critical and proactive part of this continuum, particularly for children who use the ED frequently and/or are poorly connected with their medical homes. The IMPACT DC Asthma Clinic therefore targets children who are heavily dependent on EDs for episodic care. It provides a comprehensive source of asthma education, medical care, and care coordination designed to transition patients to more effective longitudinal asthma care in their primary medical care homes. Patients are referred for consultative care from EDs, inpatient units, primary clinicians, and school nurses.

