Obstacle 2: Refusals. Families vary in their willingness to participate in research. Solutions include:

- Train research staff to appropriately present studies to families and to partner with investigators to respond to questions.
- Engage the Research Subject Advocate to empower families to make informed choices regarding research participation.

Informed Consent: Written consent will be obtained from interested study participants prior to the initiation of study activities. A single document will be used to document consent for the parents' own participation, as well as their permission for their child's participation. In addition, children age 7 and older will provide assent in accordance with Children's National's policy. The Informed Consent form that will be approved by the Children's National Health System IRB, and will supplement but not replace the dialogue between participants and research personnel. Additional requirements include:

- The Consent Form will be prepared at approximately an 8th grade reading level, with appropriate lay descriptions of technical terms wherever used.
- Participants will be allowed ample time to review the document and ask staff questions prior to deciding whether or not to participate.
- Copies of the Consent Form will be given to participants for their records.

After obtaining informed consent, study staff will administer a baseline questionnaire as described in Section D.6. Outcomes. The baseline questionnaire will be completed within ten days of consent.

Randomization: After completion of the baseline measure, the participant will be randomized to one of the study's two arms using RedCap.

Participants randomized to the intervention arm will then be provided with an orientation to the intervention, and instructed on when they will be contacted by the intervention team. These participants will also receive short-term care coordination by the IMPACT DC Asthma Clinic team

according to the Clinic’s standard protocol, and will receive periodic requests for updated contact information.

Participants randomized to the control arm will receive short-term care coordination by the IMPACT DC Asthma Clinic team according to the Clinic’s standard protocol, but will not receive any additional contact by the study team until the follow-up phone interviews with the exception of periodic requests for updated contact information.

D.6. Outcomes

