Clinical research staff will be trained in the importance of completing all data fields. Based on our prior studies, we anticipate a rate of missing data for the primary outcome of <5%. All efforts will be made to minimize patient dropout. Frequent data queries will allow us to track missing data and retrain staff as needed. Sensitivity analyses will be conducted as described above. Reasons for participant drop out will be collected and reported. In cases of missing data, we will use multiple imputation (MI) to impute the missing values.

Sample Size Considerations: Power Analysis

This study is designed to detect the smallest clinically significant difference in mean symptom free days (SFD) between the intervention and control groups.

The initial sample size calculation was based on previous data from other studies, the improvements of 0.9-1.0 SFD per 14 days are feasible, the standard deviation of SFD is 2.7, and the within subject correlation is 0.3. Power analysis was calculated for the intervention effect on SFD while justifying two assessments for each subject. The table shows the total sample size needed to detect differences in SFD from 0.9 to 1.0 with different within subject correlation. The sample size of 152 is needed to detect the difference of 1.0 SFD with standard deviation of SFD of 2.7, within subject correlation of 0.3, power of 0.8 at alpha level of 0.05. With anticipation of attrition rate of 10%, we initially planned to enroll 168 children.

The sample size was recalculated on September 14, 2015, based on the baseline data collected from the first 60 participants, which showed the following: mean was 10.25 days, median was 11.5 days, standard deviation was 4.12. The sample distribution is not normal and approximated a Poisson distribution. Based on this distribution, the calculated sample size is 188, as can achieve 80% power at a 0.05 significance level to detect a response rate ratio of 1.15 with baseline response rate 0.8. Therefore, with 10% percent attrition rate, we now plan to enroll 207 participants.

| Power Calculation with Standard Deviation of 2.7, Power of 0.8, Alpha level of 0.5 | | | |
|---|--------------------|------------|-------------------------------|
| Difference | Correlation | N | N (with 10% attrition) |
| 0.9 | 0.1 | 158 | 174 |
| 0.9 | 0.15 | 166 | 183 |
| 0.9 | 0.2 | 172 | 190 |
| 0.9 | 0.25 | 180 | 198 |
| 0.9 | 0.3 | 186 | 205 |
| 0.9 | 0.35 | 194 | 214 |
| 0.9 | 0.4 | 200 | 220 |

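### The primary t-test on symptom-free days makes no use of baseline symptom-free days, which are collected before randomisation; the test is valid, and the loss is a small to moderate amount of precision

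*Protocol*

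**What the plan says.** Protocol D.10 (aim 2) defines the primary outcome as the "time average of number of symptom-free days over a two week period (primary outcome) at 3 and 6 month follow-up" and says that "a two sample t-test will be used to compare difference of mean symptom-free days over a two week period between the two arms". No covariate is named. The next sentence adds: "Depending on the degree of dispersion, we may need to employ a Poisson or negative binomial model". No covariate is named there either.

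Baseline SFD is available. Section D.1 states: "Outcomes data will be collected by interviews at enrollment (baseline), 3 months post-enrollment, 6 months post-enrollment". Section D.5 puts the baseline interview before allocation: "After completion of the baseline measure, the participant will be randomized to one of" the two arms. The sample-size section shows that baseline SFD was recorded and used to re-size the trial, "based on the baseline data collected from the first 60 participants, which showed the following: mean was 10.25 days", with SD 4.12.

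Adjustment does appear in D.10, but only in the secondary analysis. Mixed models there will adjust for baseline covariates chosen in advance, or for those that differ between arms and bear on change in SFD. Baseline SFD is not named.

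The SAP names no primary model. Its sociodemographic control variables are "Age, gender, race, ethnicity, insurance type, parent education, household income, family medical history, parent health literacy, parental resilience". It also lists asthma severity, asthma control and ACT score as control variables, without saying whether any of them enters the primary analysis. Baseline SFD is not in that list, in the SAP's list of baseline asthma variables for interaction analyses, or in the covariate rows of the protocol's D.6 table.

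**The concern.** When the outcome is also measured before randomisation, its baseline value is often a useful predictor of the follow-up value. Including it in the primary model removes the part of the between-child variation that it explains and so narrows the confidence interval for the treatment effect. Leaving it out does not bias the comparison, because randomisation makes the unadjusted difference unbiased and its standard error already allows for chance imbalance. What is at stake is whether the interval for the main result is wider than the collected data require.

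Timing matters too. If baseline SFD is added only after outcomes have been seen by arm, the adjusted result is open to the charge that the model was chosen for its answer.

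**Working it through.** **1. Reproduce the plan's own figure.** The initial calculation uses a 1.0-day difference, SD 2.7, two assessments per child and "within subject correlation of 0.3, power of 0.8 at alpha level of 0.05", and gives 152. The mean of two visits with correlation ρ has variance SD² × (1+ρ)/2. At ρ = 0.3 the factor is 1.3/2 = 0.65. With 76 per arm the standard error is 2.7 × √(0.65 × 2/76) = 0.353, and noncentral-t power is 80.3%; 150 in total gives 79.8%. So 152 reproduces with no baseline term, and the same method returns all 21 sample sizes in the protocol table. The trial was sized for the unadjusted test.

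**2. Inputs for the check.**
- N = 188 (D.10 and SAP); 94 per arm, assuming 1:1 allocation, which is not stated.
- SD 4.12, the baseline value from the first 60 participants, assumed to hold at follow-up.
- Difference 0.15 × 10.25 = 1.5375, about 1.54 days: the rate ratio of 1.15 applied to the SAP's baseline rate of 10.25. The protocol gives that rate as 0.8.
- Correlation between the two follow-up visits 0.3 (D.10).
- Baseline-to-follow-up correlation r: not given. Range shown 0.1 to 0.3, the same at both visits.
- Two-sided 0.05; linear model; 186 degrees of freedom unadjusted, 185 adjusted.

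**3. Formulas.** With equal SDs, the covariance of baseline with the two-visit average is r × SD². Adjusting for baseline therefore leaves variance SD² × (0.65 − r²) for the average, and SD² × (1 − r²) for 6 months alone. The standard error of the difference is SD × √(factor × 2/94).

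**4. Average of 3 and 6 months.**

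| | Factor | Variance reduction | SE (days) | 95% CI half-width (days) | Power |
|---|---|---|---|---|---|
| Unadjusted | 0.65 | – | 0.485 | 0.96 | 88.4% |
| r = 0.1 | 0.64 | 1.5% | 0.481 | 0.95 | 88.9% |
| r = 0.2 | 0.61 | 6.2% | 0.469 | 0.93 | 90.3% |
| r = 0.3 | 0.56 | 13.8% | 0.450 | 0.89 | 92.5% |

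As an equivalent sample size, 188 × 0.65/(0.65 − r²) gives 191, 200 and 218, that is 3, 12 or 30 extra dyads.

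**5. Six months alone.** Hypothesis 1 in the Specific Aims and the SAP both place the primary analysis at 6 months, so this case is needed as well.

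| | Factor | Power |
|---|---|---|
| Unadjusted | 1.00 | 72.1% |
| r = 0.1 | 0.99 | 72.5% |
| r = 0.2 | 0.96 | 73.8% |
| r = 0.3 | 0.91 | 76.1% |

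**6. Sensitivity to the follow-up correlation.** For the average endpoint at r = 0.3, letting that correlation run from 0.1 to 0.4 (the range of the protocol table) gives gains of 3.4 to 4.3 points (93.0% to 96.3% at one end, 86.0% to 90.3% at the other).

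**7. Validity on a bounded scale.** In 20,000 simulated null trials of 188 children, with outcomes on 0 to 14 days, mean 10.25, SD 4.12 and all correlations about 0.3, type I error was 5.0% for the t-test and 5.1% for the adjusted model. The adjusted variance was 0.868 times the unadjusted one, against 0.56/0.65 = 0.862 from the formula.

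**The case against.** The strongest reply is that nothing here is an error. The test is valid, the sample size was derived for exactly that test, and D.10 already plans a secondary adjusted analysis that refers to change in SFD. That is right as far as it goes. But the secondary models do not name baseline SFD and do not supply the primary estimate or p-value, so the main result still comes from the less precise method.

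A second reply is that r is unknown and may be low. This stands. The baseline interview is completed within ten days of consent, before most of the care coordination that both arms receive, so baseline may predict follow-up less well than one follow-up visit predicts another. D.10 does not assign its 0.3 to the baseline pair, and near r = 0.1 the gain is negligible. Severity, control and ACT score overlap with SFD; if they were in the primary model, the further gain would be smaller.

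A third reply is that the figures are for a linear model, whereas the plan calls the distribution approximately Poisson and allows a count model. This also stands: no gain has been calculated for the count model.

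A reader might infer that the unadjusted test is biased, or that chance baseline imbalance would invalidate it. The documents do not support that: allocation is randomised and the interviewers are blinded. Nor should one assume that baseline SFD will be complete for every dyad, since participants may decline questions.

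**Conclusion.** The point holds as a matter of precision only. The primary test leaves out a pre-randomisation measurement of its own outcome, and no other part of the protocol or SAP puts it into the primary analysis. For a 1.54-day difference the cost is about 0.5 to 4 percentage points of power, and 0.01 to 0.07 days of confidence-interval half-width for the 3- and 6-month average, as r goes from 0.1 to 0.3. The power gain is similar for 6 months alone, where the starting power of 72.1% leaves less to spare.

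These figures rest on 1:1 allocation, SD 4.12 carried to follow-up, the SAP's 10.25 as the reference mean, a follow-up correlation of 0.3, and no other asthma covariate in the model. The statement that the test is valid concerns the t-test. It does not extend to a plain Poisson model, because the baseline variance-to-mean ratio is 4.12²/10.25 = 1.66.

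The change is worth making because it is nearly free, not because the planned analysis would mislead.

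**What to change.** Before outcomes are compared by arm, amend D.10 and the SAP as follows.

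- Name baseline SFD as a covariate in the primary model: a linear or repeated-measures model on arm plus baseline SFD, written for whichever primary time point is confirmed.
- Put the same term in any Poisson or negative binomial fallback.
- Handle missing baseline values by the multiple imputation that D.10 already plans.
- Keep the unadjusted t-test as a sensitivity analysis.
- State whether severity, control and ACT score enter the primary model.

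The cost is one degree of freedom for baseline SFD and a wording change in two documents. No new data are needed.
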